### 7.3 OPTICAL COHERENCE TOMOGRAPHY AND FLUORESCEIN ANGIOGRAPHY

Descriptive analysis will be conducted on the following supportive imaging endpoints:

- [Redacted bullet point]

- [Redacted]
- [Redacted]
- [Redacted]
- [Redacted]
- [Redacted]
- [Redacted]
- [Redacted]
- [Redacted]

Descriptive tables will be used for the supportive endpoints based on observed data (i.e. missing data will not be imputed).

#### 7.4 ADVERSE EVENTS

Adverse events (AEs) will be recorded starting after the first dose of study drug and continuing until 30 days after the last dose or until the last follow-up visit required by the protocol, whichever comes later.

The safety analyses on AEs will be primarily based on the Treatment-Emergent Adverse Events (TEAEs), which is defined as an AE occurring after the first injection on Day 1 (day of the first dose of study drug) and up to and including 30 days after the last dose of study drug.

All AEs will be coded using MedDRA (Version 21.0) terms.

An overview of TEAEs will be provided. A second overview of TEAEs will be provided which displays the overall summary of TEAEs by the categories ‘Study Eye’, ‘Non-Study Eye’, and ‘Non-Ocular’. In addition, the number and percentage of patients with TEAEs will be tabulated for each treatment group and in total by system organ class (SOC) and preferred term (PT). The number and percentage of the subjects who experienced at least one TEAE will be included. Subjects will only be counted once for each preferred term. In case that a subject experienced the same event more than once, the worst severity will be presented.

Tabular summaries of the following AEs will be provided by SOC and PT:

- All TEAEs regardless of the relationship to study drugs
- All TEAEs (regardless of the relationship to study drugs) with PT occurring  $\geq 5\%$  frequency based on total subjects
- TEAEs related to study drugs
- TEAEs related to injection procedure
- TEAEs by the maximum severity grade
- Systemic TEAEs
- Systemic TEAEs related to study drugs
- Systemic TEAEs related to injection procedure
- TEAEs related to study drugs by the maximum severity grade
- TEAEs related to injection procedure by the maximum severity grade
- All Ocular TEAEs by study eye
- All Ocular TEAEs by fellow eye
- Study drug related Ocular TEAEs by study eye
- Study drug related Ocular TEAEs by fellow eye
- Injection procedure related Ocular TEAEs by study eye
- Injection procedure related Ocular TEAEs by fellow eye
- Ocular TEAEs (study eye) by the maximum severity grade
- Study drug related Ocular TEAEs (study eye) by the maximum severity grade
- Injection procedure related Ocular TEAEs (study eye) by the maximum severity grade
- TEAEs leading to discontinuation of study drug
- Study drug related TEAEs leading to discontinuation of study drug
- Injection procedure related TEAEs leading to discontinuation of study drug

- Ocular TEAEs (study eye) leading to discontinuation of study drug
- TEAEs leading to death
- Study drug related TEAEs leading to death
- Injection procedure related TEAEs leading to death

Ocular TEAEs has been defined as TEAEs linked to the “Eye Disorders” system organ class and the ‘Intraocular pressure increased’ preferred term.

All AEs, including non-TEAEs, will be included in individual subject listings.

The listings will include the subject identifier, age, sex, verbatim term, preferred term, eye (N/A/OD/OS/OU), serious (yes/no), date of onset, relative study day of onset, duration of the event (or continuing), severity (mild/moderate/severe), causality (relationship to study drug/injection procedure), action taken (study drug permanently discontinued: yes/no), treatment (yes/no), and outcome (resolved /unresolved / fatal).

The same listings will be provided separately for severe AEs, AEs leading to permanent discontinuation of the study drug, and for AEs leading to death.

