12.2 Assessment and Reporting of Adverse Events

Adverse events will be recorded starting after the first dose of trial drug and continuing until 30 days after the last dose or until the last follow-up visit required by the protocol, whichever comes later. An adverse event that is ongoing at the last follow up study visit is required to be followed up until the event resolves or stabilizes at a level acceptable to the investigator and/or Sponsor.

All adverse events spontaneously reported, elicited or observed by the investigators will be recorded. The events will be recorded in the source documents and onto the adverse event pages of the case report form, including date of onset and resolution, severity, relationship to trial treatment and determination of “serious”.

Diagnostic and therapeutic non-invasive and invasive procedures, such as surgery, should not be reported as adverse events. However, the medical condition for which the procedure was performed should be reported if it meets the definition of an adverse event. For example, an acute appendicitis that begins during the adverse event reporting period should be reported as the adverse event, and the resulting appendectomy should be recorded as treatment of the adverse event.

The investigator will take all therapeutic measures necessary for resolution of the adverse event. Any medication necessary for treatment of the adverse event must be recorded in the subject’s source documents and on the appropriate pages of the subject’s case report form.

To assist with grading of adverse event severity, the following definitions are provided:

- Mild** = Aware of sign or symptom, but easily tolerated;
- Moderate** = Discomfort enough to cause interference with usual activity;
- Severe** = Incapacitating with inability to work or do usual activity;

Adverse events are assessed as either related to the intravitreal injection procedure (eyelid speculum, anesthetic drops, mydriatic drops, antibiotic drops, povidone-iodine drops or flush, subconjunctival injection of anesthetic, intravitreal injection), termed “injection procedure-related”, or to study drug (Zimura™ or Lucentis® 0.5 mg).

The relationship to the intravitreal injection procedure or to study drug will be assessed using the following definitions:

- Not Related** = There is not a reasonable possibility that the adverse event is related to the injection procedure or to the study drug.

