## 7.5 SERIOUS ADVERSE EVENTS AND DEATHS

Treatment-Emergent Serious adverse events (SAEs) will be summarized by system organ class and preferred term. The number and percentage of the subjects who experienced at least one SAE will be included.

Tabular summaries of the following SAEs will be provided:

- All SAEs regardless of the relationship to study drug
- SAEs related to study drug
- SAEs related to injection procedure
- Ocular SAEs (study eye) regardless of the relationship to study drug
- Ocular SAEs (study eye) related to study drug
- Ocular SAEs (study eye) related to injection procedure

In addition, separate listings will be created for deaths and all SAEs. List for SAEs will include the subject identifier, age, sex, verbatim term, preferred term, eye (N/A/OD/OS/OU), serious (yes/no), date of onset, relative study day of onset, duration of the event (or continuing), severity (mild/moderate/severe), causality (relationship to study drug/injection procedure), action taken (study drug permanently discontinued: yes/no), treatment (yes/no), and outcome (resolved/unresolved/fatal).

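### Do AEs that start more than 30 days after the last dose need their own incidence tables?

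*SAP*

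**What the plan says.** **Collection.** Protocol 12.2 and SAP 7.4 use the same rule. AEs are recorded from the first dose, "continuing until 30 days after the last dose or until the last follow-up visit required by the protocol, whichever comes later". The last required visit is Month 6. Protocol 12.4 applies the same period to SAEs.

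**Tabulation.** SAP 7.4 bases its AE analyses mainly on TEAEs, which run from the first injection "up to and including 30 days after the last dose of study drug". Both overviews and every table in its list are TEAE tables.

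**The remainder.** SAP 7.4 says how other events are shown: "All AEs, including non-TEAEs, will be included in individual subject listings". It adds separate listings of severe AEs, of AEs leading to permanent discontinuation and of AEs leading to death, none restricted to TEAEs.

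**SAEs.** SAP 7.5 opens with "Treatment-Emergent Serious adverse events (SAEs) will be summarized by system organ class and preferred term". Its first table is labelled "All SAEs regardless of the relationship to study drug". A further sentence says that "separate listings will be created for deaths and all SAEs".

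**The concern.** The collection period can be longer than the tabulation period. An AE starting between day 31 after the last dose and the Month 6 visit would appear in a listing but in no count by cohort, system organ class and preferred term. If it ended participation before Month 6, SAP 4.1 would count it by cohort only as a reason for non-completion.

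The trial tests no hypothesis, so the descriptive counts are its result. With 10 or 20 subjects per cohort, one subject moves an incidence by 1/10 = 10 or 1/20 = 5 percentage points.

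For SAEs, the table labels in SAP 7.5 carry no treatment-emergent qualifier, and the same phrase for all SAEs also describes an unrestricted listing. Two programmers might build different SAE tables from that text.

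**Working it through.** The plan gives no figure to reproduce here, so the check is a date count and a reading of SAP 7.5.

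**Inputs from the documents**
- Month 5 and Month 6 windows: ±7 days each (Protocol 10.2 to 10.5).
- Last dose: Month 5 D0 in Cohorts 2 and 3; Month 5 D2, two days later, in Cohorts 1 and 4.
- Planned subjects: 20 + 10 = 30 in Cohorts 3 and 2; 10 + 20 = 30 in Cohorts 1 and 4.
- TEAE cutoff: last dose + 30 days.

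**Assumptions**
- A month is M = 28, 30 or 31 days.
- Visit days are spread evenly over their windows.
- All 60 subjects are dosed at Month 5 and attend Month 6.
- The available text does not say what the windows are anchored to, so two cases are run.

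**Formula.** Days outside the tables = max(0, M − s + offset − 30), with s = 0 (Cohorts 2/3) or 2 (Cohorts 1/4).

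**Nominal dates** (offset 0). The excess is 0 in every cohort for M = 28 and M = 30. For M = 31 it is 1 day in Cohorts 2/3 and 0 in Cohorts 1/4.

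**Case A: both windows anchored to nominal dates.** The offset is w6 − w5, each from −7 to 7, giving 15 × 15 = 225 pairs.

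| M | Cohorts 2/3: mean (max) | Cohorts 1/4: mean (max) | Person-days outside | Share |
|---|---|---|---|---|
| 28 | 364/225 = 1.62 (12) | 220/225 = 0.98 (10) | 30 × 584/225 = 77.9 | 77.9/10,080 = 0.77% |
| 30 | 560/225 = 2.49 (14) | 364/225 = 1.62 (12) | 30 × 924/225 = 123.2 | 123.2/10,800 = 1.14% |
| 31 | 680/225 = 3.02 (15) | 455/225 = 2.02 (13) | 30 × 1,135/225 = 151.3 | 151.3/11,160 = 1.36% |

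The denominators are 60 × 6 × M.

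**Case B: Month 6 timed from the Month 5 D0 visit.** The offset is w6 alone, 15 values.

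| M | Cohorts 2/3: mean (max) | Cohorts 1/4: mean (max) | Person-days outside | Share |
|---|---|---|---|---|
| 28 | 15/15 = 1.00 (5) | 6/15 = 0.40 (3) | 30 × 21/15 = 42 | 0.42% |
| 30 | 28/15 = 1.87 (7) | 15/15 = 1.00 (5) | 30 × 43/15 = 86 | 0.80% |
| 31 | 36/15 = 2.40 (8) | 21/15 = 1.40 (6) | 30 × 57/15 = 114 | 1.02% |

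**Consistency with exposure.** SAP 7.1 defines treatment duration as last minus first injection date + 31. The inclusive days from first dose to last dose + 30 are (last + 30) − first + 1, which is the same quantity. With first = 1 and last = 151, both give 181. The TEAE window and the exposure period coincide.

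**Reading SAP 7.5.** The opening sentence limits the summaries to treatment-emergent events and introduces the abbreviation SAEs in the same phrase. The first label, "All SAEs regardless of the relationship to study drug", follows the pattern of the first table in SAP 7.4, which is for all TEAEs whatever their relationship to study drug. In both, the word for all refers to causality. The unrestricted wording, "separate listings will be created for deaths and all SAEs", belongs to a separate sentence about listings.

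**The case for a change.** The strongest argument for a change has three parts.

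*The protocol's own analysis section.* Protocol 11.4.4 calls for AEs to be summarised and for incidence and severity to be grouped by body system, with no 30-day limit. The word in SAP 7.4 that makes TEAEs the main basis leaves room for other tables, yet none is named. This is correct. But setting an analysis window is ordinary work for a SAP, and the protocol's sentence is also met in part by listings.

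*Many subjects could have some untabulated days.* Under the even-spread assumption, the share with at least one such day is 55/225 = 24% to 120/225 = 53% in Case A and 3/15 = 20% to 8/15 = 53% in Case B, depending on cohort and month length. That stands, but the mean is only 0.4 to 3.0 days per subject, and visits kept near target would reduce it.

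*Missed doses.* A subject who misses all Month 5 dosing but attends Month 6 would have more untabulated time. In Case A the excess is 2M − s − 30 ± 14, which runs from 56 − 2 − 30 − 14 = 10 days to 62 − 30 + 14 = 46 days. The arithmetic is right, but the documents give no frequency. Protocol 10.6 sends subjects who withdraw to the Early Withdrawal assessments, and those who start another NVAMD treatment before completing dosing are no longer evaluated under the protocol. Long off-dose follow-up is not an evident planned path, though it is not excluded.

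Extra tables would also have a cost. Post-dose observation would differ between subjects and would be nominally 2 days shorter in Cohorts 1 and 4, while the TEAE tables give everyone the same tail.

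**Conclusion.** No change to the plan is needed. SAP 7.4 states a collection period, a shorter analysis period and what happens to events in between. That is a fair and declared trade-off: a uniform 30-day tail, aligned with exposure, in exchange for showing a few later events in listings only. Every AE, SAE and death remains visible to the reader of the report. Month 6 acuity, eye examination, IOP, laboratory, vital-sign and ECG results have their own summaries in SAP 7.2 and 7.6 to 7.9.

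About 0.4% to 1.4% of person-days lie outside the tables. This rests on months of 28 to 31 days, an even spread over ±7 days, and full dosing and attendance at Months 5 and 6. It says nothing about how many events would fall in those days, and it would be larger if subjects stopped dosing but stayed to Month 6.

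In SAP 7.5, the opening sentence fixes the scope of the SAE tables. The missing qualifier is a clerical matter that table titles can carry when the outputs are programmed. Full additional tables by system organ class and preferred term would cover almost the same follow-up as the TEAE tables and add little.

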11 STATISTICAL METHODS

11.1 Experimental Design

There will be 4 dosing cohorts in this trial. Approximately 60 subjects will be enrolled; 10 subjects in cohorts 1 and 2, and 20 subjects in cohorts 3 and 4.

Cohort 1

Administered for a total of 6 times (Day 1 – Month 5), in the following sequence, 2 days apart:

- D0: Lucentis[®] 0.5 mg/eye
- D2: Zimura[™] 4 mg/eye (administered as two injections of Zimura 2 mg)

Cohort 2

Administered for a total of 6 times (Day 1 – Month 5), in the following sequence:

- Lucentis[®] 0.5 mg/eye followed by Zimura[™] 2 mg/eye on the same day

Cohort 3

Induction Phase: Administered for a total of 3 times (Day 1 – Month 2), in the following sequence, 14 days apart:

- D0: Lucentis[®] 0.5 mg/eye followed by Zimura[™] 2 mg/eye on the same day
- D14: Zimura[™] 2 mg/eye

Maintenance Phase: Administered for a total of 3 times (Month 3 - Month 5), in the following sequence:

- Lucentis[®] 0.5 mg/eye followed by Zimura[™] 2 mg/eye on the same day

Cohort 4

Induction Phase: Administered for a total of 3 times (Day 1 - Month 2), in the following sequence, 14 days apart:

- D0: Lucentis[®] 0.5 mg/eye followed by Zimura[™] 2 mg/eye on the same day
- D14: Zimura[™] 2 mg/eye

Maintenance Phase: Administered for a total of 3 times (Month 3 - Month 5) in the following sequence, 2 days apart:

- D0: Zimura™ 2 mg/eye
- D2: Lucentis® 0.5 mg/eye followed by Zimura™ 2 mg/eye on the same day

All subjects will have a final follow-up visit at Month 6.

The first 10 subjects will be enrolled into Cohort 1 according to the procedures noted below.

The first three subjects will be assigned to Cohort 1 (Lucentis® 0.5 mg and Zimura™ 4 mg). Once the 3rd subject completes a safety period of one week after the first dose of Zimura™ 4 mg without the occurrence of a dose limiting toxicity as defined in Section 9.2.3 Dose Limiting Toxicity, full enrollment of Cohort 1 may commence.

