### 7.1 EXTENT OF EXPOSURE

Exposure to each study medication will be evaluated for each cohort and overall with respect to treatment duration (= Last injection date – First injection date + 31, in days), number of subjects treated at each planned visit, total injections received, using descriptive statistics (N, mean, standard deviation, median, minimum, Q1, Q3, maximum).

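### Procedure-related and study-eye ocular TEAEs are planned only as percentages of subjects, with no event counts or exposure rates, although planned injections per subject range from 12 to 18

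*SAP*

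**What the plan says.** SAP 7.4 gives the number and percentage of subjects with TEAEs by system organ class and preferred term, for each cohort and in total. Its counting rule is "Subjects will only be counted once for each preferred term"; where a subject has the same event again, the worst severity is shown. The table list includes "TEAEs related to injection procedure" and versions of it for study eye, fellow eye, systemic events, severity, discontinuation and death. SAP 7.5 adds two procedure-related SAE tables. No event count or exposure-based rate is specified in SAP 7.4, SAP 7.5 or Protocol 11.4.4. SAP 7.4 also promises two overview tables, whose content it does not describe.

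SAP 7.1 covers exposure by cohort, including "total injections received, using descriptive statistics", but does not link it to adverse events.

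Protocol 11.1 sets the regimens:

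- Cohort 1: "Administered for a total of 6 times (Day 1 – Month 5), in the following sequence, 2 days apart", with Zimura 4 mg "administered as two injections of Zimura 2 mg".
- Cohort 2: "Administered for a total of 6 times (Day 1 – Month 5), in the following sequence", one Lucentis and one Zimura injection on the same day.
- Cohorts 3 and 4: "Induction Phase: Administered for a total of 3 times (Day 1 – Month 2), in the following sequence, 14 days apart", followed by three maintenance cycles that differ between the two cohorts.

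All cohorts have their final visit at Month 6.

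**The concern.** The trial's only objective is safety, and SAP 3.3.1 sets the four cohorts side by side in columns. An injection-procedure event needs an injection, or at least an injection visit, to occur. Cohorts with more of either have more chances to record one over the same six months, so a higher subject percentage may reflect only those extra chances. The table also treats a subject with one conjunctival haemorrhage like a subject with six. Recurrence is part of what a more intensive regimen costs the patient, and it would be visible only in the listings. SAP 2.3 says the study should inform the design of later controlled trials, so a reader will want to know whether a higher percentage is more than extra injections alone would produce.

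**Working it through.** The documents state no total of injections per subject and no per-injection risk, so there is no planned figure to reproduce. The check counts injections from Protocol 11.1 and then applies assumed risks.

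**1. Planned exposure per subject**

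| Cohort (n) | Injections | Injection days | Zimura injections | Zimura mg |
|---|---|---|---|---|
| 1 (10) | 6×(1+2) = 18 | 6×2 = 12 | 12 | 24 |
| 2 (10) | 6×(1+1) = 12 | 6×1 = 6 | 6 | 12 |
| 3 (20) | 3×(2+1) + 3×2 = 15 | 3×2 + 3×1 = 9 | 9 | 18 |
| 4 (20) | 3×(2+1) + 3×(1+2) = 18 | 3×2 + 3×2 = 12 | 12 | 24 |

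Planned cohort totals are 180, 120, 300 and 360 injections (960 in all) and 120, 60, 180 and 240 injection days.

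**2. Expected subject percentage with no difference in risk**

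With the same independent risk p at each of k exposures, the share of subjects with at least one event is 1 − (1 − p)^k.

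| Assumed p | Cohort 2 | Cohort 3 | Cohorts 1 and 4 |
|---|---|---|---|
| 1% per injection | 11.4% | 14.0% | 16.5% |
| 3% per injection | 30.6% | 36.7% | 42.2% |
| 1% per injection day | 5.9% | 8.6% | 11.4% |

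**3. Repeat events lost**

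At 3% per injection, Cohort 4 expects 360 × 0.03 = 10.8 events, but its any-event line shows 20 × 0.422 = 8.4 subjects. Cohort 2 expects 120 × 0.03 = 3.6 events and shows 10 × 0.306 = 3.1 subjects. The loss is larger where there are more injections.

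**4. How often the pattern would be seen**

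Exact binomials with n = 20 and n = 10, and equal per-injection risk, give these chances for Cohort 4's observed percentage against Cohort 2's.

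| Assumed p per injection | Higher | Tied | Lower |
|---|---|---|---|
| 1% | 60% | 13% | 27% |
| 2% | 66% | 10% | 24% |
| 5% | 73% | 8% | 19% |

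The gradient is therefore a matter of expectation, not of every result.

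**5. What a rate can and cannot show**

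Every cohort has 6 Lucentis injections, and Zimura always comes in 2 mg injections. Total injections therefore equal 6 + (Zimura mg)/2: 6+12 = 18, 6+6 = 12, 6+9 = 15, 6+12 = 18. Injection days equal the number of Zimura injections in every cohort.

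- If every event came from Zimura at risk q per Zimura injection, events per injection would be 12/18, 6/12, 9/15 and 12/18 of q, that is 0.67q, 0.50q, 0.60q and 0.67q.
- If risk attached to the injection day, the per-injection pattern would be the same: 0.67, 0.50, 0.60 and 0.67 of the daily risk.
- Conversely, if risk attached to the needle, events per injection day would be 1.5, 2.0, 1.67 and 1.5 times the needle risk.

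Neither denominator is neutral, and neither isolates the drug.

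**6. Cohort 3 count**

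The Cohort 3 schedule in SAP 3.1 marks Lucentis at D14 as well as D0. That would give 3×(2+2) + 3×2 = 18 injections. SAP 2.2, Protocol Section 3 and Protocol 11.1 place it at D0 only, which gives 15. The table in step 1 and the exact relation in step 5 follow the regimen text.

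**The case against.** The strongest reply is that injection number is part of each regimen, so the percentage of subjects affected over six months is a legitimate target. The study is descriptive, tests nothing and does not claim per-injection comparability. This stands, and the subject tables should not be replaced.

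A second reply is that the plan already separates study-drug-related from procedure-related events by causality assessment, reports injection totals in SAP 7.1 and lists every event with onset date and causality. This stands in part. A reader could build a rate by hand, but no rate or event count is specified for any table.

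A third is imprecision. One event in 120 injections has an exact Poisson 95% interval of about 0.02 to 4.6 per 100; four in 360 has about 0.3 to 2.8. Intervals that allow for clustering within 10 to 20 subjects would be unreliable. This is why no interval is asked for.

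Three stronger readings are tempting, but the documents do not support them:

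- **That the percentages will differ between cohorts.** This holds only in expectation (step 4), and Cohorts 1 and 4 have equal counts.
- **That a per-injection rate would show whether Zimura or the needle is responsible.** The design links the two exactly (step 5).
- **That the effect can be sized from OPH2001.** Protocol 4.5.2 reports 15 of 47 subjects (32%) with procedure-related events on a five-injection schedule. Read as equal independent risks, this gives 1 − (32/47)^(1/5) = 7.4% per injection, and 60%, 68% and 75% of subjects at 12, 15 and 18. It carries a result from another disease and schedule, and assumes that events do not cluster in susceptible subjects. It is illustrative only.

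**Conclusion.** The point holds as a gap in reporting, not as an analysis error. The planned tables validly describe whole-regimen risk. They also discard repeat events and are expected to rise with injection count alone. Between 12 and 18 injections the expected difference is about 5 percentage points at an assumed 1% risk (16.5 − 11.4 = 5.1) and about 12 at 3% (42.2 − 30.6 = 11.6). In a cohort of 10, that is roughly half a subject to just over one subject.

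These sizes rest on an assumed constant, independent risk per injection, which the documents do not give. Clustering of events within subjects would reduce the gradient, and risk that goes with the injection day would change it. Protocol 12.2 counts the speculum, drops and povidone-iodine as part of the procedure, so the injection day is a plausible unit. The change is worth making because safety is the only objective and the data are already planned.

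**What to change.** In SAP 7.4, keep all per-subject tables. For injection-procedure-related TEAEs and study-eye ocular TEAEs, add by cohort:

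- the number of events, repeats included;
- events per 100 injections actually received, from the SAP 7.1 totals summed over both drugs;
- events per 100 injection days actually given, from the injection dates.

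Present these as descriptive figures, with no confidence interval required. Add a note that the rates assume roughly constant risk per unit of exposure, that part of the procedure may go with the visit rather than the needle, and that no rate can separate a Zimura effect from a procedure effect because injection count and cumulative Zimura dose are linked by design. State also what the two overview tables contain.

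Reconcile the Cohort 3 schedule in SAP 3.1 with SAP 2.2, Protocol Section 3 and Protocol 11.1. Using injections actually received keeps the rates from depending on the planned count.

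The cost is one or two tables from data already collected and a short note. The risk is that readers over-interpret the rates, so they should sit beside the subject percentages rather than stand alone.

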## 3.3 DATA HANDLING CONVENTIONS

### 3.3.1 General Conventions

Data will be analysed using SAS (Version 9.4 or later) or R. Descriptive analyses will be performed on baseline, safety data. All tables will be created with the 4 dosing cohorts presented in columns, unless otherwise specified.

Descriptive statistics will be tabulated as follows:

- Categorical data will be summarized in contingency tables presenting frequencies and percentages.
- Continuous data will be summarized using number of non-missing values (n), mean, standard deviation, median, minimum, 1st quartile (Q1), 3rd quartile (Q3), and maximum values.

Listings with individual Subjects' data will be provided for all CRF (including derived data) and central laboratory data or other external data. Data collected on the CRF that are *not* present in a table will also be listed (e.g. time and method of tonometry, comments fields, data on Fatal Outcomes page, Unscheduled Visit pages, etc.).

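### SAP 7.4 decides whether an adverse event is ocular by coding alone, so a study-eye event coded outside that rule drops out of the study-eye tables

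*SAP*

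**What the plan says.** SAP 7.4 gives one definition: "Ocular TEAEs has been defined as TEAEs linked to the “Eye Disorders” system organ class and the ‘Intraocular pressure increased’ preferred term". The tables that depend on it are split by eye, for example "All Ocular TEAEs by fellow eye" and "Ocular TEAEs (study eye) leading to discontinuation of study drug".

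The eye is also a planned field in the individual adverse event listings: "verbatim term, preferred term, eye (N/A/OD/OS/OU), serious (yes/no". SAP 7.5 has the same field in its listing of serious events.

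Three neighbouring outputs have no stated rule:

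- The second overview "displays the overall summary of TEAEs by the categories ‘Study Eye’, ‘Non-Study Eye’, and ‘Non-Ocular", but how an event is placed in a category is not said.
- There are three systemic tables, including "Systemic TEAEs related to injection procedure", but systemic is not defined.
- SAP 7.5 lists three ocular tables of serious events, including "Ocular SAEs (study eye) related to injection procedure", without a definition of its own.

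Under SAP 3.3.1, "All tables will be created with the 4 dosing cohorts presented in columns, unless otherwise specified".

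**The concern.** Safety is the trial's only objective, and both drugs are given by repeated injection into one eye. A reader will expect the study-eye tables to hold every study-eye adverse event. Under the stated rule they hold only those whose coding meets the test. The authors added one preferred term to the organ class, which suggests they saw that the class alone does not capture every eye event. They gave no general rule for the rest.

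The general tables are not a full substitute. They do not separate the eyes, and SAP 7.4 counts a subject once per preferred term at the worst severity, so the same term in both eyes becomes one entry. Protocol 9.3 allows treatment of neovascular AMD in the fellow eye throughout the study, so fellow-eye events from non-study injections are possible. What may be understated is the study-eye incidence by organ class and preferred term.

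**Working it through.** The plan gives no figure of its own here. The check is a count of the tables listed in SAP 7.4 and 7.5.

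**Step 1. TEAE tables in SAP 7.4.** 13 general + 3 systemic + 10 ocular = 26. The 10 ocular tables are:

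- Study eye, 7: all events; drug-related; procedure-related; each of these three again by maximum severity; and events leading to discontinuation.
- Fellow eye, 3: all events; drug-related; procedure-related.

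**Step 2. Tables that one study-eye event would enter if classed as ocular.** Let D = 1 if related to drug, P = 1 if related to the injection procedure, S = 1 if it led to discontinuation, and 0 otherwise. Every event enters the all-events and maximum-severity tables. Each type of relatedness adds two tables, and discontinuation adds one:

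tables = 2 + 2D + 2P + S

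| Event | Tables missed, S = 0 | Tables missed, S = 1 |
|---|---|---|
| Unrelated | 2 | 3 |
| Related to drug only, or procedure only | 4 | 5 |
| Related to both | 6 | 7 |

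An event coded outside the rule enters none of these, so the figures are the tables it misses. Protocol 12.2 describes relatedness in either/or terms and does not say whether one event can be related to both. If it cannot, the last row is empty and the range is 2 to 5. If it can, the maximum is 7.

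**Step 3. Fellow eye.** Tables = 1 + D + P, which is 1 to 2, or 3 if related to both.

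**Step 4. Serious events in SAP 7.5.** 3 general + 3 ocular study-eye = 6. If the 7.4 rule carries over, a serious study-eye event misses 1 + D + P ocular tables: 1 to 2, or 3 if related to both.

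**Step 5. What one omitted subject does to a row.** This is an illustration only. It uses the planned sizes in SAP 2.3 and assumes that all subjects are treated.

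- Cohort 1 or 2: 1/10 = 10.0% becomes 0/10.
- Cohort 3 or 4: 1/20 = 5.0% becomes 0/20.
- Total: 1/60 = 1.7% becomes 0/60.

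**Step 6. How many events are affected.** This cannot be calculated. It depends on the MedDRA hierarchy, which is not in the documents, and on whether linkage means the primary organ class or any linked class. The second reading leaves out no more events than the first, and possibly fewer.

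**The case against.** The strongest reply is that no affected event can be shown. A reader might infer that endophthalmitis would be missing, because the protocol telephones subjects about it after injections and Protocol 4.5.3 reports one serious case in an earlier study. The documents do not say how that term is coded, so they do not support the inference. This part of the reply stands.

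A reader might also infer that such events vanish from the report. They do not. They remain in the general TEAE and serious-event tables by cohort, and in listings that show the eye. They may also be counted in the second overview. SAP 7.2 summarises visual acuity loss. SAP 7.7 covers intraocular pressure and shift tables for anterior chamber cells, vitreous haze, vitreous haemorrhage and peripheral retina. None of these depends on event coding. That also stands, although those summaries carry no event term, relatedness or seriousness, so they do not restore the study-eye event tables.

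A third tempting reading is that each such event is lost from all seven study-eye tables. Seven needs one event that is related to both drug and procedure and leads to discontinuation, and Protocol 12.2 may not allow the first condition.

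Finally, a coding-based definition is explicit and reproducible, whereas an eye-based one needs a complete eye field. That is a fair cost, and the fix allows for it. It does not answer the gap in the rule.

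**Conclusion.** The concern holds as a gap in a definition. Followed exactly, SAP 7.4 leaves any study-eye event coded outside its rule out of 2 to 5 of the 7 study-eye tables, or up to 7 if an event may be related to both drug and procedure. The count is certain given the listed tables; the number of events is unknown and could be zero.

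Three consequences are conditional. The serious-event tables are affected only if the rule carries over to SAP 7.5. The overview would disagree with the ocular tables only if it uses the recorded eye. A study-eye event would be tabulated as systemic only if systemic means everything not ocular under this rule.

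No data are lost and no hypothesis test is involved. The point should still be fixed, because these tables present study-eye safety by term and cohort in a trial whose only purpose is safety.

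**What to change.** Replace the definition in SAP 7.4 with one rule:

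- **Ocular** (TEAEs and serious events): any event with the eye recorded as OD, OS or OU, whatever its organ class. Add any event with the eye missing or N/A that meets the present organ class or preferred term rule, taking linkage as primary or any linked class.
- **Eye:** assign study or fellow eye from the recorded eye, with OU counted in both. Query ocular events with no recorded eye, and show unresolved ones as eye not specified.
- **Systemic (non-ocular):** all other events.

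Apply this rule to the ocular and systemic tables in 7.4, the serious-event tables in 7.5 and the overview by eye category, and settle it before database lock. The cost is a short SAP text, minor programming and a completeness check on a field already planned for the listings.
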